5.5 Concomitant medication

Medications specifically prohibited in the exclusion criteria are not allowed during the ongoing trial. These would include anti-coagulation therapy (e.g. Lovenox, warfarin, etc.), estrogen/progesterone therapy (including hormonal contraceptives) and other anti-GBM agents (including investigational ones). If patient is on avastin at the time of enrollment on the study, he/she will be allowed to remain on this to prevent rebound and potential difficulty interpreting results. If there is a clinical indication for one of these or other medications specifically prohibited during the trial, discontinuation from trial therapy may be required.

5.6 Study Procedures

Before initiating progesterone therapy, throughout the course of progesterone therapy, and following progesterone discontinuation, various clinical and diagnostic evaluations are outlined. The purpose of obtaining these detailed measurements is to ensure adequate **safety and tolerability assessments** as well as **efficacy assessments**. Clinical evaluations and laboratory/radiographic studies may be repeated more frequently, if clinically indicated. The Schedules of Assessments during the screening, treatment and post-treatment phases of study are summarized in **Section 1.3**.

Screening Phase

Screening procedures will be performed up to 14 days prior to initiation of progesterone therapy unless otherwise specified. All subjects must first read, understand, and sign the IRB-approved ICF before any study-specific screening procedures are performed. After signing the ICF, completing all screening procedures, and being deemed eligible for entry, subjects will be enrolled in the study. Procedures that are performed prior to the signing of the ICF and are considered standard of care may be used as screening assessments if they fall within the screening window.

The following procedures will be performed during the **Screening Phase**:

- Obtaining informed consent
- Review of eligibility criteria (including documentation of pathologic diagnosis of GBM)
- Medical history and demographics
- Complete physical exam (including neurologic assessment)
- Determining score on Karnofsky Performance Scale (KPS, **Appendix 1**)
- Vitals signs, weight and height
- Review of concomitant medications (including steroid and anti-seizure med documentation)
- MRI brain w/ and w/o contrast (show at least 1 cm³ of progressing enhancing tumor)
- QOL assessments
- Serum sample for exploratory biomarkers
- Clinical laboratory tests for:
 - CBC with differential
 - Complete metabolic panel (CMP)
 - Serum or urine pregnancy test (for female subjects of childbearing potential (FCBP) only)

Treatment Phase

Patients will receive subcutaneous natural progesterone at the dose called for on study on daily basis for up to 24 weeks during the **Treatment Phase**. The following procedures are to be conducted during the **Treatment Phase** of the study while the patient is receiving progesterone therapy.

- Brief medical history, symptom-directed physical exam including KPS and neurologic assessment (on day 15, on day 29, every 4 weeks thereafter). Can be performed at ± 3 days during first 8 weeks and ± 7 days thereafter.
- Vitals signs, weight (on day 15, on day 29, every 4 weeks thereafter). Can be performed at ± 3 days during first 8 weeks and ± 7 days thereafter.
- Review of concomitant medications (including steroid and anti-seizure med documentation, every week during 1st 4 weeks, every 4 weeks thereafter). Can be performed at ± 3 days during first 8 weeks and ± 7 days thereafter.
- Drug diary documentation by patient (to be collected every two weeks when patient return to get new supply of medication).
- MRI brain w/ and w/o contrast (after 4 weeks, after 8 weeks, every 8 weeks thereafter). Can be performed at ± 1 week at the after 4 weeks MRI and ± 2 weeks thereafter.
- Adverse event (AE) assessment (every week during 1st 4 weeks, every 4 weeks thereafter). Can be performed at ± 3 days during first 8 weeks and ± 7 days thereafter.
- QOL assessment after 4 weeks ± 3 days, after 8 weeks ± 1 week, after 24 week ± 2 weeks (assess for final time if patient comes off study before 24 weeks and it is > 2 weeks from previous assessment).
- Serum sample for exploratory biomarkers after 4 weeks ± 3 days.
- Pharmacokinetic assessment on day 1 (0, 30 minutes, 1, 2, 4, 6, 8 hrs from drug injection) as well as at day 8 prior to drug injections (only in first 3 patients at each dose level). (May alternatively be done on any day after the 1st week during the initial 4 weeks with no need for day 8 trough draw if done later)
- Clinical laboratory tests for:
 - CBC with differential
 - CMP

Post-Treatment Phase

The **Post-Treatment Phase** is the period after progesterone is stopped to the end-of-study (EOS) visit. The EOS visit will be scheduled 28 days after discontinuation of progesterone (window for visit can be up to 2 weeks beyond 28 days).

The following will be performed at the EOS visit:

- Brief medical history, physical exam including KPS and neurologic assessment.
- Vitals signs, weight.
- Review of concomitant medications (including steroid and anti-seizure med documentation).
- AE assessment.
- Clinical laboratory tests for CBC with differential and CMP.

While patients will not be further followed for official study visits after the EOS visit, further data for PFS and OS endpoints may be obtained based on chart review of future standard-of-care visits with the subject's treating physician(s).

5.7 Description of Study Procedures

Medical history

Findings from medical history (obtained at screening) and physical examination shall be given a baseline grade according to the procedure for AEs. Increases in severity of pre-existing conditions during the study will be considered AEs, with resolution occurring when the grade returns to the pre-study grade or below.

Physical examination

Physical examinations should be conducted according to the Schedules of Assessments. Full physical examinations should be conducted at screening/baseline and the EOS visit (evaluate all major organ systems, including the following categories: general, head, eyes, ears, mouth/throat, neck, heart, lungs, abdomen, lymph nodes, joints, extremities, integumentary, neurologic, and psychiatric). Other examinations may be focused, at the discretion of the Investigator, to identify changes from baseline or evaluate changes based on the patient's clinical symptoms. Weight is to be recorded at each visit, height at screening/baseline visit only.

Neurological assessment

Will be assessed with timing according to the Schedules of Assessments. Although not used for determining response, it is useful to evaluate improvement in the neurologic exam, as compared with the baseline assessment, that should coincide with objective measurement of tumor size.

NEURO EXAM STATUS (compared to pre-treatment exam)	
Better	Must be on stable or decreasing dose of steroids
Same	Failure to qualify for better or worse
Worse	Include patients requiring increasing steroid doses to remain stable

Performance status assessment

Patients will be graded with timing according to the Schedules of Assessments on the Karnofsky Performance Scale (**Appendix 1**).

Vital signs

Vital signs (blood pressure [BP], pulse, temperature, and respiration rate) will be evaluated according to the Schedules of Assessments. Body weight is also recorded along with vital signs.

Clinical laboratory tests

The following clinical laboratory tests will be performed (see Schedules of Assessments):

- CBC with differential
 - Includes hemoglobin/hematocrit, white blood cells with automated differential, platelets
- Complete metabolic panel (CMP)
 - Includes sodium, potassium, bicarbonate, chloride, BUN, creatinine, calcium, glucose, total bilirubin, SGOT (AST), SGPT (ALT), alkaline phosphatase, albumin, total protein
- Pregnancy test (female subjects of childbearing potential (FCBP) only)
 - Criteria for those not considered FCBP
 - Age \geq 55 years and one year or more of amenorrhea
 - Age $<$ 55 years and one year or more of amenorrhea, with estradiol $<$ 20 pg/ml
 - Age $<$ 55 with prior hysterectomy but intact ovaries, with estradiol $<$ 20 pg/ml
 - Prior bilateral oophorectomy

Toxicity (Adverse Event) assessment

Toxicities will be scored according to CTCAE v5.0. Evaluations for toxicity will be performed weekly during the 1st 4 weeks of progesterone therapy followed by every 4 weeks thereafter (through a total of up to 24 weeks drug therapy). Final assessment (EOS visit) will be 4 weeks after last drug dose.

MRI brain with and without contrast

Diagnostic brain MRI scans with and without contrast will be utilized to assess for response with timing according to the Schedules of Assessments. DSC perfusion imaging will also be obtained, if possible, but is not required. Volumetric assessment of progressive measurable contrast-enhancing disease ($\geq 1 \text{ cm}^3$) will be performed at baseline. If there is no measurable disease at trial baseline scan (e.g. gross resection of all recurrent enhancing disease), patient is still eligible for study but will be assessed for progression based on criteria for non-evaluable disease ($< 1 \text{ cm}^3$ of recurrent enhancing disease).

Imaging response criteria is defined below:

Measurable Disease: Measurable lesions are those with clearly defined margins by contrast-enhanced MRI scan that is at least 1 cm^3 in volume. All measurable lesions will be considered together. Clear enhancing lesions representing progressive tumor pre-treatment that is less than 1 cm^3 in volume will be considered non-evaluable disease.

Objective Status, To Be Recorded at Each Evaluation: Unless progression is observed, objective status can only be determined when ALL measurable sites and lesions are assessed.

Response Definitions:

- **Complete Response (CR):** Complete disappearance of all measurable disease in contrast-enhancing MRI. No new lesions. No evidence of non-evaluable disease. All measurable lesions and sites must be assessed using the same techniques as baseline. Patients must be on no steroids. If there is no enhancing disease present at baseline, then this criteria will not apply and the case will not be considered in the N when evaluating for % of patient achieving CR.
- **Partial Response (PR):** (Measurable disease only) Greater than or equal to 65% decrease under baseline in total tumor volume of all measurable lesions. No progression of non-evaluable disease (defined as progression to at least 1.5 cm^3 in volume). No new lesions. All measurable lesions and sites must be assessed using the same techniques as baseline. If there is only non-evaluable disease or no enhancing disease present at baseline, then this criteria will not apply and the case will not be considered in the N when evaluating for % of patient achieving PR.
- **Stable Disease (SD):** Does not qualify for CR, PR, or progression. The designation of SD requires a minimum of 8 weeks duration (2 assessment of stable disease from baseline at least 4 weeks apart). All measurable sites must be assessed using the same techniques as baseline. The steroid dose at the time of the scan evaluation should be no greater than the maximum dose used in the first 8 weeks from initiation of therapy.
- **Progressive Disease (PD):** 40% increase in the tumor volume of all measurable lesions over previous exam (over baseline if no decrease) using the same techniques as baseline, OR clear progression of non-evaluable disease (defined as growth to at least 1.5 cm^3 in volume), OR clear appearance of any new measurable lesion/site, OR clear clinical worsening or failure to return for evaluation due to death or deteriorating condition (unless clearly unrelated to this cancer).

Best Response: This will be calculated from the sequence of objective statuses. For patients with all disease sites assessed every evaluation period, the best response will be defined as the best objective status as measured according to the above criteria.

Pharmacokinetic Testing (Research)

Protocol Title: Pilot study of progesterone for recurrent GBM

Number of patients tested: The first three patients of a treatment dose level will be undergo pharmacokinetic testing for plasma level of progesterone.

Timing of Assessments: Pharmacokinetic samples will be obtained on day 1 of therapy. Plasma samples will

be obtained immediately prior to administration of drug and, subsequently, at 30 minutes, 1 hour, 2 hour, 4 hours, 6 hours, and 8 hours after drug injection. Additional sample will be obtained prior to the day 8 injection. (May alternatively be done on any day after the 1st week during the initial 4 weeks with no need for day 8 trough draw if done later)

Sample testing: After collection of plasma samples from three patients at one dose level (8 specimens/patient, 3 patients/dose level), batched samples will be sent to an internal Emory lab for testing of progesterone levels.

Quality-of-Life (QOL) Testing (Research)

These questionnaires have been validated in the brain tumor population and used in other large, prospective studies for this patient population, providing a good potential comparison group for patients on this study. Subjects can opt out of this assessment if they so choose.

Timing of Assessments: Initial evaluations will be performed ≤ 14 days before starting natural progesterone. Subsequent evaluations will be at the following time points after initiation of study therapy (4 weeks \pm 3 days, 8 weeks \pm 1 week, 24 weeks \pm 2 weeks) with one final off-study evaluation if it is prior to the 24 week evaluation and > 2 weeks from previous evaluation (this evaluation would be the visit when patient comes off study).

QOL Questionnaires: EORTC Quality of Life Questionnaire-Core 30/Brain Cancer Module-20 (EORTCQLQ30/BN20); M. D. Anderson Symptom Inventory Brain Tumor Module (MDASI-BT) (**Appendix 2**)

Potential intrinsic tumor biomarkers (Research)

In our pre-clinical studies, progesterone treatment was shown to exert anti-tumor effects on glioblastoma via different growth/survival pathways involved in proliferation, vascularization/angiogenesis, glycolytic/oxidative metabolism, and apoptosis.

To evaluate these factors within the tumor, the glioblastoma tumor specimen from the time of initial diagnosis will be assessed for the following factors (performed either as part of the original neuropathologic assessment or from subsequent assessment of the original tissue block/slides). These factors will be correlated with outcomes of patients on study to determine if there are detectable associations with response to progesterone.

- **Progesterone receptor (PR-A and PR-B)** – To be determined by immunohistochemistry of glioblastoma tumor from original surgery with expression level reported on a scale of 0-4 [Atif et al. 2011].
- **MGMT methylation** – This will be determined by methylation-specific PCR with results reported as positive, negative or borderline. All patients originally diagnosed at Emory has this test performed as part of the routine neuropathologic assessment. Will plan to use results from original pathology report unless it was not performed in which case the original tumor tissue block will be obtained for this testing [Atif et al. 2019].
- **Mutations in the following genes (p53, EGFR, PTEN, AKT, IDH1, IDH2)** – Sequence variation at hotspots within these genes will be assessed via a SnapShot Cancer Mutation Panel. All patients originally diagnosed at Emory have this test performed as part of the routine neuropathologic assessment. We plan to use results from the original pathology report unless it was not performed; in which case, the original tumor tissue block will be obtained for this testing [Atif et al. 2015a; Atif et al. 2015b; Atif et al. 2019].
- **Genomic loss/gain particularly at the following loci (1p, 1q, 7p, 10q, 19q)** – Copy number variation of the entire genome will be assessed via the Oncoscan SNP Microarray Analysis. All patients originally diagnosed at Emory have this test performed as part of their routine neuropathologic

assessment. We will use results from the original pathology report unless it was not performed in which case the original tumor tissue block will be obtained for this testing.

Potential serum biomarkers (Research)

We propose to test a panel of circulating biomarkers to evaluate the effect of progesterone treatment on glioblastoma progression. The levels of these proposed biomarkers have been correlated with glioblastoma progression and survival in a number of clinical studies.

Serum will be obtained within 14 days prior to the start of treatment and at the 4 weeks blood draws after initiation of treatment. The initial and changes in levels of these biomarkers will be correlated with outcomes of patients on study to determine if there are detectable associations with response to progesterone. ELISA or Multiplexed fluorescent microsphere immunoassay will be performed to measure the levels of the following biomarkers:

- YKL-40 [Hormigo et al. 2006; Iwamoto et al. 2011]
- Matrix Metalloproteinase-9 (MMP-9) [Hormigo et al. 2006]
- Glial Fibrillary Acidic Protein (GFAP) [Jung et al. 2007]
- C-Reactive Protein (CRP) [Strojnink et al. 2014]
- Soluble CD14 [Zhou et al. 2010]
- Soluble CD23 [Zhou et al. 2010]

6. Data and Specimen Banking

Blood samples and GBM tumor specimen (paraffin block or unstained slides from previous surgery) will be obtained and used for medical research by the investigators of this study. *Data and specimens from this study may be useful for other research being done by investigators at Emory or elsewhere. To help further science, Investigators may provide de-identified data and/or specimens to other researchers. Any information that could identify participants will not be included. If data or specimens are labeled with study ID, we will not allow other investigators to link that ID to identifiable information.*

Samples and data collected under this protocol may be used to study **GBMs or other cancers**. Access to stored samples will be limited to IRB-approved investigators. Samples and data will be stored using codes assigned by the investigators or their designees. Data will be kept in password-protected computers. Only investigators will have access to the samples and data.

All stored samples will be maintained in the laboratory to which it was sent initially for analysis and will be kept indefinitely unless destruction is requested by study participant or after conclusion of the study at such point where study investigators have deemed that there is no further use for the samples. Study participants who request destruction of samples will be notified of compliance with such request and all supporting details will be maintained for tracking.

The results of some study tests and procedures will be used only for research purposes and will not be placed in subject's medical record. For this study, those items include: research blood assessment and research tumor specimen assessment.

7. Sharing of Results with Participants

In general, study staff will not provide any individual results to subjects (ex. outcome trial results or results from subject's samples studies). If something of urgent medical importance to the participating subjects will be found, the PI (or co-Is) will inform the subject, although we expect that this will be a very rare occurrence. Samples and data will only be used for research.

8. Study Timelines

The current plan is to complete enrollment to this study (up to 32 patients) over 2 years with up to 1 year additional followup time for a total of 3 years to enroll and follow patients per study specifications.

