1.3 Schedule of Assessments

Tests and procedures	Pre-reg	≤14 days prior to start of therapy	Initial 4 weeks of progesterone therapy				Second 4 weeks of progesterone therapy	Subsequent maintenance progesterone therapy
			d1	d8	d15	d22	d29	Beginning of every 4 week interval to study end (up to 24 wks of therapy) ¹⁰
Informed consent	X							
Path diagnosis	X							
H&P, KPS		X ⁴			X ⁵		X ⁵	X ⁶
Height (only initially), Weight		X			X ⁵		X ⁵	X ⁶
Neuro assessment		X			X ⁵		X ⁵	X ⁶
Adverse event assessment			X	X ⁵	X ⁵	X ⁵	X ⁵	X ⁶
Medical History	X							
Concomitant medication	X	X	X	X ⁵	X ⁵	X ⁵	X ⁵	X ⁶
Initial Consult	X ³							
CBC w/diff		X					X ⁵	X ⁶
CMP ¹		X					X ⁵	X ⁶
Exploratory serum biomarkers		X					X ⁵	
Pharmacokinetic assessment			X ⁸	X ⁸				
MRI w/ & w/o contrast ²		X					X ⁵	X ⁷
Steroid/anti-Sz med documentation		X	X	X ⁵	X ⁵	X ⁵	X ⁵	X ⁶
QOL assessments		X					X ⁵	X ⁹
Pregnancy test		X ¹¹						
Drug diary documentation			X ¹²		X ¹²		X ¹²	X ¹²

Note – AE assessments, concomitant medications and steroid/anti-Sz med documentation at d8 and d22 may be done by telephone, if the patient does not otherwise need to be seen in clinic.

¹ Comprehensive Metabolic Panel (CMP) - Sodium, potassium, bicarbonate, chloride, BUN, creatinine, calcium, glucose, total bilirubin, SGOT (AST), SGPT (ALT), alkaline phosphatase, albumin, total protein (Standard care). The frequency of CMP will be up to the treating physician's discretion.

² Standard diagnostic brain MRI w/ & w/o contrast.

³ Initial consultation by either neuro-oncology or radiation oncology can be completed ≤ 21 days before initiation of therapy.

⁴ May be satisfied by H&P at initial consultation if within 14 days of starting therapy.

⁵ May be assessed ± 3 days.

⁶ May be assessed ± 7 days. Final followup (including AE assessment) will be at 28 days after last drug dose.

⁷ To be assessed after 8 weeks of therapy ± 1 week and then every 8 weeks ± 2 weeks, thereafter. Other MRIs can be done at discretion of treating physician, if needed.

- ⁸ To be performed on day 1 (0, 30 minutes, 1, 2, 4, 6, 8 hrs from drug injection) as well as at day 8 prior to drug injections on those days only in patients getting PK evaluations. (May alternatively be done on any day after the 1st week during the initial 4 weeks with no need for day 8 trough draw if done later)

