Timing of Assessments: Initial evaluations will be performed \leq 14 days before starting natural progesterone. Subsequent evaluations will be at the following time points after initiation of study therapy (4 weeks \pm 3 days, 8 weeks \pm 1 week, 24 weeks \pm 2 weeks) with one final off-study evaluation if it is prior to the 24 week evaluation and $>$ 2 weeks from previous evaluation (this evaluation would be the visit when patient comes off study).

QOL Questionnaires: EORTC Quality of Life Questionnaire-Core 30/Brain Cancer Module-20 (EORTCQLQ30/BN20); M. D. Anderson Symptom Inventory Brain Tumor Module (MDASI-BT)

2. Objectives (and Endpoints)

Our main goal is to establish pharmacokinetics, safety/tolerability and efficacy of daily subcutaneous natural progesterone for the treatment of patients with recurrent glioblastoma. The specific objectives/endpoints of this study are listed below.

OBJECTIVES	ENDPOINTS
Primary	

Protocol Title: Pilot study of progesterone for recurrent GBM

OBJECTIVES	ENDPOINTS

To determine that the pharmacokinetics of natural progesterone given to recurrent GBM patients by subcutaneous injection is consistent with previous determinations made using the aqueous formulation of progesterone (IBSA Institut Biochimique SA, Lugano, Switzerland) given subcutaneously.To determine the safety of administering daily subcutaneous natural progesterone for the treatment of patients with recurrent GBMs.To determine the ORR [defined as stable disease (SD) or better (PR or CR)] at 8 weeks in eligible patients with recurrent GBM treated with daily subcutaneous natural progesterone.	
Pharmacokinetic: Plasma progesterone levels at 0, 30 min, 1, 2, 4, 6, 8 hrs from 1st injection and at 8 prior to drug injection in 3 pts at each dose level. (May alternatively be done on any day after the 1st week during the initial 4 weeks with no need for day 8 trough draw if done later)Safety: Adverse events, clinical assessments (eg. vital sign, physical, etc.), clinical laboratory test.Efficacy: Overall response rate (ORR) per protocol volumetric definition at 8 weeks from initiation of progesterone.
Secondary	

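### The stable-disease timing rule does not fit the permitted MRI windows: non-progressing patients scanned in window can fall outside every response category at week 8, and Sections 1.3 and 5.6 give different windows

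*Combined protocol and SAP*

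**What the plan says.** **Endpoint.** Section 2 (Objectives and Endpoints) gives the primary efficacy objective as ORR, "defined as stable disease (SD) or better (PR or CR"), and the endpoint as "Overall response rate (ORR) per protocol volumetric definition at 8 weeks from initiation of progesterone". Sections 5.2 and 15.1 apply the same 8-week ORR to the first 10 patients at the expansion dose: 2 or more successes and enrolment continues; 1 or none and the study is declared futile.

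**SD rule.** Section 5.7 defines SD as not qualifying for CR, PR or progression, and adds: "The designation of SD requires a minimum of 8 weeks duration (2 assessment of stable disease from baseline at least 4 weeks apart"). It also requires the same techniques as at baseline and sets a limit on steroid dose.

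**Scan timing, Section 1.3.** The d29 MRI carries footnote 5, "May be assessed ± 3 days". The next MRI carries footnote 7: "To be assessed after 8 weeks of therapy ± 1 week and then every 8 weeks ± 2 weeks, thereafter".

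**Scan timing, Section 5.6.** MRIs are due "after 4 weeks, after 8 weeks, every 8 weeks thereafter", and the window is: "Can be performed at ± 1 week at the after 4 weeks MRI and ± 2 weeks thereafter". The week-8 scan comes after the week-4 scan, so it falls under the wider allowance.

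**Cross-reference.** Section 5.7 says that MRI "will be utilized to assess for response with timing according to the Schedules of Assessments", which points to Section 1.3.

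**The concern.** The two scans that must establish SD by week 8 are nominally exactly as far apart as the minimum. If the week-8 scan is earlier, relative to its target day, than the week-4 scan was, the gap is below 28 days, even with both scans in window. No section says how to classify such a patient when there is no progression and no CR or PR.

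Two outcomes are possible. Applied literally, the rule makes the patient a non-success because of scan dates alone. Otherwise someone decides the case after seeing the scan, in an uncontrolled single-arm trial. The futility boundary is 2 of 10, so one or two such patients could decide whether enrolment stops. SD matters particularly for patients with no enhancing disease at baseline after surgery: Section 5.7 removes them from the CR and PR assessments, so SD is their only route to success.

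**Working it through.** The plan states no proportion expected to miss the rule, so there is no figure to reproduce. The check is of the dates the plan allows.

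**Inputs.** Take first dose as d1. Week-4 scan: d29 + A. Week-8 scan: d57 + B.
- Section 1.3: A from -3 to +3, B from -7 to +7.
- Section 5.6: A from -7 to +7, B from -14 to +14.
- SD rule (Section 5.7): gap at least 28 days; duration at least 56 days.

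**1. Permitted gaps.** Gap = (57 + B) - (29 + A) = 28 + B - A.
- Section 1.3: 28 - 7 - 3 = 18 to 28 + 7 + 3 = 38 days.
- Section 5.6: 28 - 14 - 7 = 7 to 28 + 14 + 7 = 49 days.

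Example: d31 (A = +2) and d55 (B = -2) are in window under both sections. The gap is 55 - 31 = 24 days.

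**2. Can the rule always be met in window?** Take the latest week-4 scan.
- Section 1.3: d32 + 28 = d60, within the limit of d64.
- Section 5.6: d36 + 28 = d64, within the limit of d71.

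So a compliant week-8 date always exists, but no section tells sites to book for it.

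**3. Share of pairs under 28 days.** The rule fails when B < A. *Assumption not in the documents:* A and B are independent and uniform over whole days.
- Section 1.3: 7 × 15 = 105 pairs, 7 ties; (105 - 7)/2 = 49 fail; 49/105 = 46.7%.
- Section 5.6: 15 × 29 = 435 pairs, 15 ties; (435 - 15)/2 = 210 fail; 210/435 = 48.3%.

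Other assumptions, using truncated normal dates with SD one third to one half of the half-window:

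| Scan dates | Gap under 28 days |
|---|---|
| Centred on target | 42-47% |
| Week-8 scan late by half its half-window | 6-19% |
| Week-8 scan early by half its half-window | 76-89% |
| Week-8 scan always booked at least 28 days after week 4 | 0% |

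**4. The 8-week duration.**
- Counted from first dose, any week-8 scan with B < 0 fails. Under uniform dates, failing gap or duration is 55/105 = 52.4% (Section 1.3) or 238/435 = 54.7% (Section 5.6).
- Counted from the baseline MRI, which may precede first dose by up to 14 days, the test may not bind. Under Section 1.3 the earliest week-8 scan is 56 - 7 = 49 days after first dose, so a baseline MRI at least 7 days before dosing gives at least 56 days.

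**5. Effect on the futility look (illustration).** P(pass) = P(X ≥ 2), X ~ Binomial(10, p(1 - q)), where p is the true SD-or-better rate, all of it SD, and q is the share of stable patients lost. Neither p nor q is in the documents.

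| p | q | p(1 - q) | P(pass) |
|---|---|---|---|
| 0.25 | 0 | 0.250 | 0.76 |
| 0.25 | 0.25 | 0.1875 | 0.59 |
| 0.25 | 0.467 | 0.133 | 0.39 |
| 0.30 | 0 | 0.300 | 0.85 |
| 0.30 | 0.467 | 0.160 | 0.49 |
| 0.40 | 0 | 0.400 | 0.95 |
| 0.40 | 0.467 | 0.213 | 0.66 |

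The q = 0.25 row is what results if half of all pairs are exactly 28 days apart and the rest split evenly either side.

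**The case against.** **Rule and windows can be met together.** This is correct (step 2). The lack of slack is a property of the nominal dates, and a site that books the second scan from the first avoids the problem. But nothing in the plan asks for that, and the windows as written allow shorter gaps.

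**Scan dates may cluster.** Patients return every two weeks for drug and are assessed at 4-week intervals. If MRIs follow that rhythm, exact 28-day gaps would be common, whereas the uniform model under Section 1.3 gives them only 7/105 = 6.7%. This stands, and it is why the percentages are only illustrative.

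**Section 1.3 governs.** Section 5.7 refers response MRI timing to the Schedules of Assessments, so the 7-to-49-day range is probably not operative. That is fair, but Section 5.6 still gives sites different windows, and Section 1.3 alone allows 18 days.

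**The duration clause may be harmless.** The SD text mentions baseline, and PFS runs from the pre-treatment MRI. On that reading the 8-week test often does not bind. The gap test does not depend on the start point.

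**Later scans could confirm SD.** Extra MRIs are allowed and a week-16 scan follows, but a later scan does not settle status at the 8-week endpoint.

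**A stronger reading.** A reader might infer that about half of on-schedule patients will miss SD, or that the chance of passing futility will fall from 0.76 to 0.39. The documents support neither. Both need an assumed scan-date distribution, and the second also needs an assumed true rate made up entirely of SD. The gap rule does not apply to CR or PR.

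**Conclusion.** The point holds as an inconsistency in the primary endpoint. The SD rule demands at least 28 days between two assessments. The stated windows permit 18 days (Section 1.3) or 7 days (Section 5.6). Those sections conflict for both scans, the start of the 8 weeks is undefined, and a non-progressing patient with a short gap has no category. These statements rest on the text alone.

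The frequency does not. It is 47-48% under independent, evenly spread dates, and anywhere from 0% to 76-89% under other plausible booking patterns. The futility figures are conditional on an assumed true rate as well. They show that the 2-of-10 rule is sensitive to a few reclassified patients; they do not predict what will happen.

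**What to change.** 1. **One set of MRI windows.** Reconcile Sections 1.3 and 5.6, noting that Section 5.7 already defers to the Schedules of Assessments.
2. **Make the SD timing rule consistent with that set**, by either:
   - requiring the week-8 MRI to be at least 28 days after the week-4 MRI, which is always possible within either set of windows. Cost: a narrower booking window for the second scan; or
   - defining 8-week SD by the in-window week-4 and week-8 scans, without a separate day count. Cost: it accepts shorter gaps, down to 18 days under Section 1.3, which leaves less time for a 40% volume increase to appear.
3. **State the start of the 8 weeks** (baseline MRI or first dose), and how a non-progressing patient who still misses the rule is counted in the ORR and at the interim look.
4. **Keep the steroid-dose and same-technique conditions** of the present SD definition.
5. **Make the change before the interim futility look**, so that no patient's status is settled after the scan is known.

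This is a wording change in Sections 1.3, 5.6 and 5.7, with no extra scans.
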